Title	BETTER CARE – HF: Building Electronic Tools To Enhance and Reinforce Cardiovascular Recommendations – Heart Failure
Short Title	BETTER CARE – HF: Building Electronic Tools To Enhance and Reinforce Cardiovascular Recommendations – Heart Failure
Brief Summary	This study will test two types of electronic health record (EHR)-based alerts to improve guideline-adherent care for patients with heart failure and reduced ejection fraction (HFrEF). Alerts will be triggered for patients with ejection fraction (EF) \leq 40% who are not on guideline-recommended medical therapy. The two types of alerts tested will be a Best Practice Alert (BPA) and an electronic message.
Objectives	To test two types of EHR-based alerts that promote appropriate medical therapy for patients with HFrEF.
Methodology	Prospective cohort study
Endpoints	Primary endpoint: medication prescribing patterns Secondary endpoint: hospitalization and mortality
Study Duration	Eighteen months
Participant Duration	Eighteen months
Population	Patients with EF \leq 40%
Study Sites	One single health system, NYULH, consists of approximately 60 outpatient cardiology practices.
Number of participants	Up to 2000 participants
Statistical Analysis	We will begin all analyses with descriptive summary statistics and graphical displays of all variables. Primary analyses will utilize McNemar's tests for medication prescriptions and patient outcomes of hospitalization and mortality. We will adjust for patient demographics and clinical characteristics, as well as provider-level characteristics, such as demographics, panel size, insurance mix, and sub-specialty training.

CONFIDENTIAL

This material is the property of the NYU School of Medicine and Langone Medical Center. Do not disclose or use except as authorized in writing by the study sponsor

Schematic of Study Design

CONFIDENTIAL

This material is the property of the NYU School of Medicine and Langone Health. Do not disclose or use except as authorized in writing by the study sponsor

1 Introduction, Background Information and Scientific Rationale

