5.2 Participant Withdrawal or Termination

Not applicable as the subjects are recruited at the clinic level.

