For patients meeting the eligibility criteria, a message in the EHR will automatically be sent to the provider. The provider will receive either a Best Practice Alert (BPA) or electronic message indicating that their heart failure patient is not on guideline-recommended therapy. The message will offer guidance for physician decision-making regarding HFrEF care. The study team presented the proposed project to the NYULH MCIT Project Portfolio Review Committee on February 11, 2021 and was approved to work with MCIT to build the electronic messages. Providers will be notified through the Weekly Epic Update and in presentations to medical directors that they may see the alert prior to the start of the study.

Patients' clinical outcomes will be monitored through EHR data collection for 18 months. Data collection will include elements of protected health information including patient name, medical record number, address zip code, and service dates. These will be necessary for data linkages and in order to track patients for receipt of intervention and clinical outcomes. All PHI data will be kept on a secure NYULH server and destroyed at the earliest possible point. Data on the patient's medication prescription, hospitalization, hospitalization for HF, and mortality will be recorded as study outcomes. The study team members will not collect this information directly; data will be collected in NYULH's EHR system, EPIC, and an EPIC Reporting analyst from DataCore will extract the relevant parameters from the EHR into a report.

Data points that will be collected for research purposes
Medication prescription
Hospitalization
Hospitalization for HF
Mortality
Name
Medical record number
Address zip code
Service dates

Provider survey data will be anonymously collected via Qualtrix. No identifiable information, PII, or health information will be collected. The URLs for the survey are below:

BPA version = https://nyumc.yul1.qualtrics.com/jfe/preview/previewId/f42fb1cb-b997-4fb8-8f60-9e311e6b6320/SV_7P3UhfVSH6KgpuK?Q_CHL=preview&Q_SurveyVersionID=current

IBM version = https://nyumc.yul1.qualtrics.com/jfe/preview/previewId/c97ab951-3feb-478a-8af8-a53e9abbe02d/SV_7PQoQunPLM8I8ZU?Q_CHL=preview&Q_SurveyVersionID=current

8 Safety and Adverse Events

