9.1 Study Hypotheses

Patient in clinics receiving the EHR-based alerts will have higher rates of adherence to guideline recommended medical therapy.

Providers will like the EHR-based alerts and will want to continue to use them in their practice.

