9.2 Sample Size Determination

In order to have 80% power to detect a 10% improvement in prescribing for each intervention arm vs. control, we will require a total of at least 1503 patients (501 per arm). Based on prior data, we estimate that alerts will trigger for a sample between 1500-2000 patients, but are unable to accurately control the specific number of patients due to fluctuating clinical volume at practices.

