9.3 Statistical Methods

We will begin all analyses with descriptive summary statistics and graphical displays of all variables. Primary analyses will utilize McNemar's tests for medication prescriptions and patient outcomes of hospitalization and mortality. We will adjust for patient demographics and clinical characteristics, as well as provider-level characteristics, such as demographics, panel size, insurance mix, and sub-specialty training.

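### Section 9.3 makes no allowance for correlation among patients of the same clinic or provider, so its arm-versus-control tests are anti-conservative for any positive intracluster correlation

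*Combined protocol and SAP*

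**What the plan says.** The analysis is set out in section 9.3 and repeated in the Protocol Summary: "Primary analyses will utilize McNemar's tests for medication prescriptions and patient outcomes of hospitalization and mortality". The next sentence reads "We will adjust for patient demographics and clinical characteristics, as well as provider-level characteristics, such as demographics, panel size, insurance mix, and sub-specialty training". No model is named for that adjustment. Sections 9.2 and 9.3 and the Protocol Summary mention no ICC, design effect, random effect, GEE, robust variance or cluster-level analysis.

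Other sections place exposure above the patient:

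- Section 9.1, the hypothesis: "Patient in clinics receiving the EHR-based alerts will have higher rates of adherence to guideline recommended medical therapy".
- Section 5.2, on withdrawal: "Not applicable as the subjects are recruited at the clinic level". Section 11.3 likewise bases the consent waiver on participation by clinic, and section 5 refers to practice sites that were chosen or selected.
- Section 7, on delivery: "The provider will receive either a Best Practice Alert (BPA) or electronic message indicating that their heart failure patient is not on guideline-recommended therapy". Section 5.3 describes mailing lists of cardiologists specific to the alerts they received, with no need to self-select, and section 7 gives a separate survey version for each alert type.
- Protocol Summary: "One single health system, NYULH, consists of approximately 60 outpatient cardiology practices".

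Section 9.2 frames the comparison as "80% power to detect a 10% improvement in prescribing for each intervention arm vs. control", with 501 patients per arm and 1503 in total. It expects 1500 to 2000 patients.

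**The concern.** The primary outcome is a prescriber's decision. Patients of one cardiologist, or of one practice, share that prescriber's habits and, on the natural reading of the documents, the same alert condition. A chance difference in habits between the practices in two arms can then pass for an alert effect.

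McNemar's test treats pairs as independent and takes no covariates. Adjusting for provider demographics, panel size, insurance mix and training removes only the part of the shared variation that those variables explain. The remaining correlation still goes uncounted in the standard error.

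At stake is the validity of the p-value for each alert type against control. The direction of the error is the same for prescribing, hospitalization and mortality. This is separate from the question of what McNemar's test is meant to pair: an ordinary unpaired test or ordinary logistic regression in its place would carry the same fault.

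**Working it through.** **The plan's own figure.** The 501 per arm in section 9.2 cannot be reproduced, because alpha, control rate and ICC are not given. For a 10-point difference at two-sided 5% and 80% power, an unclustered two-proportion formula needs at most 392 per arm (412 with continuity correction), at a control rate of about 45%. Several unstated choices come within 3% of 501, among them a smaller alpha and a paired formula. A hidden design effect would also fit: 501/392 = 1.28, or ICC about 0.012 at 25 patients per practice. So 501 does not show whether clustering was considered in 9.2.

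**Inputs for the error rate.**

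- From the documents: about 60 practices (Protocol Summary), three arms, 1503 to 2000 patients (the 9.2 minimum and the stated ceiling).
- Derived: 1503/60 = 25.05 and 2000/60 = 33.3 patients per practice.
- Assumed: equal practice sizes, 20 practices per arm, two-sided alpha 5%, ICC from 0.005 to 0.10.

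**Formulas.** With m patients per cluster, the design effect is DE = 1 + (m − 1) × ICC. The actual type I error of a test that ignores clustering is 2 × [1 − Φ(1.96/√DE)].

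Example, low end: m = 25.05, ICC 0.01. DE = 1 + 24.05 × 0.01 = 1.24; 1.96/√1.24 = 1.76; error 7.8%.

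Example, high end: m = 33.3, ICC 0.05. DE = 1 + 32.3 × 0.05 = 2.62; 1.96/√2.62 = 1.21; error 22.6%.

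| Assumed ICC | Error, 25 per practice | Error, 33 per practice |
|---|---|---|
| 0.005 | 6.4% | 6.9% |
| 0.01 | 7.8% | 8.8% |
| 0.02 | 10.7% | 12.7% |
| 0.05 | 18.7% | 22.6% |
| 0.10 | 28.8% | 34.1% |

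**Check by simulation.** Beta-binomial data, 20 practices of 25 patients per arm, 20,000 runs:

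| Assumed ICC | Unpaired test between arms | McNemar, patients paired across arms | McNemar, before/after within patients |
|---|---|---|---|
| 0.01 | 7.5% | 7.7% | 5.2% |
| 0.02 | 10.9% | 10.9% | 6.3% |
| 0.05 | 18.5% | 18.5% | 7.7% |
| 0.10 | 29.2% | 29.0% | 11.0% |

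At ICC 0 the unpaired test gave 4.9%, as it should. The last column further assumes 20% discordant pairs, with the ICC applied to the direction of change.

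**If the provider is the cluster.** Assume 5 to 10 patients per provider and ICC 0.05. For m = 5, DE = 1.20 and the error is 7.4%. For m = 10, DE = 1.45 and the error is 10.4%.

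**Unequal practices.** Using 1 + ((CV² + 1)m − 1) × ICC with m = 25.05 and an assumed CV of 0.7, the error is 9.3% at ICC 0.01 and 24.3% at 0.05.

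**A test that respects the cluster.** In a separate simulation with 20 practices of 25 patients per arm and a 35% control rate, a t-test on practice-level rates held 4.4% to 5.5%.

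**The case against.** The strongest reply is that the size of the error is not in the documents. Without an ICC, a reader might infer that the false-positive rate is known to be far above 5%. It is not: at ICC 0.005 it is 6% to 7%, and even the nominal 5% is an assumption, since no alpha is stated. That objection stands as to size. It does not touch the direction, which holds for any positive ICC.

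Second, allocation by clinic is implied rather than stated. Section 7 is worded by provider, the Protocol Summary calls the study a prospective cohort, and the design schematic is not available in the text reviewed. This too stands, and the calculation changes with the unit. Smaller provider clusters lower the inflation at a given ICC, although the ICC among patients of one provider could be higher. Under either unit, patients who share a prescriber appear to share the alert condition.

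Third, McNemar's test may be meant before and after within patients, where the inflation is much smaller. But a within-patient change in one arm does not answer the arm-versus-control question in 9.2. Pairing patients across arms brings back nearly the full inflation.

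Fourth, a reader might infer that planned confidence intervals are too narrow. The plan specifies none. The point concerns the tests; intervals come into it only if they are built on the same independence assumption.

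Fifth, the figures rest on one layout. Section 5 speaks of selected sites, so the number of practices taking part may not be 60. Hospitalization and mortality may have other rates and ICCs, so the percentages need not carry over to them.

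**Conclusion.** The point holds and should be corrected before analysis. As written, 9.3 and the Protocol Summary prescribe tests that ignore a correlation which the described delivery of the alerts makes likely. This is an analysis that would mislead if followed, rather than a missing detail.

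For a between-arm test, the actual error is about 8% to 23%, given two-sided 5%, 60 equal practices split 20 per arm, 25 to 33 patients each and ICC 0.01 to 0.05. It is about 6% to 7% at ICC 0.005, and about 7% to 10% for provider clusters of 5 to 10 patients at ICC 0.05. None of these ICCs comes from the documents. They do not support a single error rate stated as fact, nor a claim that 501 per arm was computed without regard to clustering.

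**What to change.** In section 9.3 and the Protocol Summary:

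1. State the unit allocated to each alert type or control: clinic or provider.
2. Replace McNemar's test for every arm comparison with an analysis that respects that unit. One option is a mixed logistic model or GEE clustered on it, with a small-sample correction suited to binary data. (Kenward-Roger was developed for linear mixed models and is only approximate here.) The other is an analysis of cluster-level rates, with degrees of freedom taken from the actual number of clusters. The covariates already listed can enter the model.
3. Report the ICC for each outcome.

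In section 7, add practice and provider identifiers to the list of data points to be extracted. They are not on it now.

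The cost is revised wording, two more extracted fields and slightly more analysis work. Intervals from the new analysis will be wider than those from an unclustered one, and correct. Making the test valid needs no extra patients; whether 501 per arm still gives 80% power is a separate question for 9.2.

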5.3 Provider Survey Recruitment

For the provider survey, we will recruit cardiologists who received the BPA or electronic message through emails (see attachment). They will be made aware that completing the survey is completely anonymous and will in no way impact their employment. The recruitment emails will be sent via listservs of cardiologist who received the BPAs and electronic messages. These listservs are specific for those cardiologists who received BPAs or electronic messages and the survey does not require cardiologists to self-select whether they received a BPA or a message. Only cardiologists who received a BPA or electronic message will be contacted. We will send an initial recruitment email and a subsequent follow up email.

The consent form will be attached to the email. It will also be available via link within the first question in Qaltrix. The first question in Qaltrix asks the provider to review the consent document and requires the provider to click a button stating that they are consenting to participate before being shown the remaining survey questions. If the provider does not click this button, they will not be able to move forward or complete the survey.

6 Study Schedule

Participants will be included in this study by virtue of meeting eligibility criteria and having a patient encounter during the study period. There are no study-specific visits. Any patient meeting criteria who has one or more patient encounters during the study period will be included. Therefore, no study-specific visits are relevant for this study, so there is no schedule of visits.

CONFIDENTIAL

This material is the property of the NYU School of Medicine and Langone Health. Do not disclose or use except as authorized in writing by the study sponsor

7 Study Procedures / Evaluations

There are no study-specific procedures that patients will undergo. They will receive care as usual by their outpatient providers. The EHR algorithm developed by the study team identifies eligible patients with EF \leq 40% on most recent echocardiogram, and exclusion criteria listed above. The EHR algorithm will also capture information on demographics, diagnoses in the patient's problem list, prescription history, allergies, EF, and relevant lab results.

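### Section 9.3 does not name baseline prescribing, at patient or practice level, as a covariate for a prescribing outcome compared between clinics, and names no between-arm model to carry it

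*Combined protocol and SAP*

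**What the plan says.** Section 9.3 and the Protocol Summary carry the same short analysis paragraph. The primary method is: "Primary analyses will utilize McNemar's tests for medication prescriptions and patient outcomes of hospitalization and mortality". The adjustment sentence follows: "We will adjust for patient demographics and clinical characteristics, as well as provider-level characteristics, such as demographics, panel size, insurance mix, and sub-specialty training". The clinical characteristics are not itemised, the provider items are examples, and no model is named.

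Other sections bear on the point:

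- Section 3.3 defines the outcome as prescription of a beta-blocker, an ACE-I/ARB/ARNI and/or an MRA, at encounter level.
- Section 7 lists what the algorithm captures, including "prescription history, allergies, EF, and relevant lab results".
- Section 9.1 states the hypothesis by clinic: "Patient in clinics receiving the EHR-based alerts will have higher rates of adherence". Section 5.2 also describes recruitment at clinic level.
- Section 9.2 sizes the study, at 501 per arm, to "detect a 10% improvement in prescribing for each intervention arm vs. control".
- The Protocol Summary says alerts go to patients "who are not on guideline-recommended medical therapy", and Section 9.2 counts its 1500-2000 patients as those for whom an alert triggers. Section 4.2 does not require a patient to be off therapy, and Section 6 includes any eligible patient with an encounter.

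**The concern.** When the outcome is current prescribing, earlier prescribing is an obvious candidate covariate. Practices can differ in prescribing habit, and if alerts are assigned by clinic, each arm's follow-up rate partly reflects the habits of its clinics. A baseline difference between arms could then be read as an alert effect, or could hide one. The listed items, such as panel size and insurance mix, are indirect substitutes.

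The wording also allows baseline prescribing to be put in or left out after the data are seen. And the adjustment sentence is attached to no analysis that could use it: McNemar's test takes no covariates. At stake are protection against baseline imbalance and, depending on who is analysed, an appreciable share of the precision available from 501 patients per arm.

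**Working it through.** **1. The plan's own figure.** The 501 per arm cannot be reproduced, because alpha and the control rate are not stated. For a 10-point difference with 80% power, the largest n per arm at any control rate is 392 at two-sided alpha 0.05 (412 with continuity correction) and 474 at 0.025 (494 with correction). Exactly 501 appears at two-sided 0.0167 with a control rate of 35% or 55%, none of which is stated. Below, 501 per arm is simply taken to give 80% power.

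**2. How large could a baseline gap be?** Inputs from the documents: 501 per arm and about 60 practices, so m = 1503/60, about 25 patients per practice if all take part. Assumed: 30% baseline prescribing, ICC 0 to 0.10, and allocation unrelated to practice habit.

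SD of gap = sqrt(2 × 0.30 × 0.70 × [1 + (m − 1) × ICC] / 501)

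| ICC | SD of gap (points) | Chance of a gap above 5 points |
|---|---|---|
| 0 | 2.9 | 8% |
| 0.01 | 3.2 | 12% |
| 0.05 | 4.3 | 25% |
| 0.10 | 5.3 | 35% |

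**3. Case A: the analysis set mixes users and non-users of the class.** Assumed: 40% on the class at baseline, 92% of users continue, 10% of non-users start.

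- Follow-up rate = 0.40 × 0.92 + 0.60 × 0.10 = 0.428.
- Baseline-outcome correlation = (0.92 − 0.10) × sqrt(0.40 × 0.60 / (0.428 × 0.572)) = 0.81.
- Standard-error ratio, adjusted to unadjusted = sqrt(1 − 0.81²), about 0.58, or about 42% smaller, ignoring clustering.
- With 20 practices of 25 patients per arm and a between-practice SD of 0.3-0.6 on the logit scale, one cluster simulation gave 3.8-5.1 points unadjusted and 2.4-2.6 adjusted (38-48% smaller). A second gave 3.9-5.2 and 1.9-2.0 (about 51-62% smaller).
- Shift from a 5-point baseline gap = 0.05 × (0.92 − 0.10) = 0.041, or about 4 points against a 10-point target.

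For other correlations ρ, power at 501 per arm = Φ((1.960 + 0.842)/sqrt(1 − ρ²) − 1.960), ignoring clustering:

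| ρ | Power | n per arm for 80% |
|---|---|---|
| 0 | 80% | 501 |
| 0.3 | 83.6% | 456 |
| 0.5 | 89.9% | 376 |
| 0.7 | 97.5% | 256 |

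**4. Case B: every analysed patient is off the class at baseline.** Patient status is then constant. It gains nothing (the ρ = 0 row), and there is no patient-level gap to correct. Only the practice's earlier rate can help:

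SE ratio = sqrt(1 − f × r²)

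Here f is the between-practice share of the variance of a practice mean, and r is the practice-level correlation between the earlier rate and later starting. Assumed: 10% start, 25 patients per practice, logit SD 0.3-0.6, r 0.3-0.7.

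- Between-practice variance = (0.09 × 0.3)² = 0.00073 to (0.09 × 0.6)² = 0.0029. Within-practice variance = 0.09/25 = 0.0036. So f = 0.17 to 0.45.
- SE ratio = sqrt(1 − 0.17 × 0.09) = 0.99 to sqrt(1 − 0.45 × 0.49) = 0.88.

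Simulation gave 0.99 to 0.89, a gain of about 1-11%.

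**5. Does McNemar's test already deal with this?** The pairing is not defined. If each patient is paired before and after, baseline status is in the test, but the test then assesses change within patients and not each alert arm against control. In neither reading does it hold the Section 9.3 covariates.

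**The case against.** The strongest reply is that the large figures describe Case A, whereas the Protocol Summary and Section 9.2 tie the sample to patients not on therapy. If each class is analysed in patients not taking it, the patient-level covariate is useless and the 4-point shift does not arise. This stands as a limit on size. It does not settle the matter: Section 4.2 does not require being off therapy, and with three classes counted, a patient missing one may be taking the others.

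A second reply is that the unitemised clinical characteristics, or the open provider list, may already include baseline prescribing. They may. The fair statement is that it is not named. Wording that permits either choice is still not pre-specification.

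A third is that McNemar's test may already condition on baseline. That holds only under before-after pairing, which leaves the comparison sized in Section 9.2 unaddressed.

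A reader might also infer several stronger claims that the documents do not support:

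- **That baseline prescribing is excluded, or is the strongest predictor.** The text excludes nothing, and no predictor strength is given.
- **That imbalance would arise by chance across 20 practices per arm.** The readable text does not describe randomisation, the Protocol Summary calls the design a prospective cohort study, and Section 5 refers to chosen practice sites, so the number taking part is unknown. Without random allocation, baseline differences could be systematic, which makes adjustment more important.
- **That both covariates are already in hand.** Section 7 covers eligible study patients; a practice rate before go-live needs an additional query.

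**Conclusion.** The concern holds in a limited form. Baseline prescribing is not named at patient, provider or practice level, and no between-arm model is named to carry it. Its value depends on the undefined analysis set: roughly 40% or more off the standard error and protection against a shift of about 4 points in a mixed set with 40% already on the class, but only about 1-11% off the standard error, plus correction of practice-level imbalance, if all are off it. The continuation and start rates, practice variation and correlations are assumptions, because the documents give none. An unconditional claim that the plan wastes much of its precision would go too far. The gap does not invalidate the study, but it is worth closing because the remedy is cheap. Confidence is medium.

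**What to change.** In Section 9.3 and the Protocol Summary:

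1. Define the analysis set for each drug class, and state that each alert arm is compared with control by a regression model that accounts for clustering by practice or other allocation unit. If McNemar's test is kept, define its pairs and give it a secondary, within-arm role.
2. Adjust that model for (a) the patient's prescription status for the class at or before the index encounter, wherever it varies in the analysis set; and (b) the practice's class-specific prescribing rate among eligible patients in a fixed period before go-live, for example 12 months. Keep (b) even if the analysis is restricted to patients not on the class.
3. Itemise the remaining patient and provider covariates.

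Admission in the same earlier period could be added for the hospitalization outcomes; this is optional and its benefit was not quantified.

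The cost is protocol wording and one retrospective Epic query, with no new patients or procedures.
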